6.2 Timing of Evaluations

6.2.1 Screening and Pre-Entry Evaluations

Screening and pre-entry evaluations must occur prior to the **participant** starting any study medications, treatments, or interventions.

Screening

Screening evaluations to determine eligibility must be completed within 30 days prior to study entry unless otherwise specified. In addition to data being collected on **participants** who enroll into the study, demographic, clinical, and laboratory data on screening failures will be captured in a Screening Failure Results form and entered into the ACTG database.

Pre-Entry

Pre-entry evaluations must be completed at least 24 hours after screening evaluations have been completed and within 7 days prior to the entry visit.

The pre-entry and screening visits may be combined in the event the **participant** presents with the following: Documentation of HIV-1 status and the results of an HIV-1 RNA level performed at a CLIA-certified laboratory \leq 30 days prior to study entry.

6.2.2 Entry Evaluations

Entry evaluations must occur at least 24 hours after pre-entry/screening evaluations unless otherwise specified. All entry evaluations must be performed after successful randomization and completed prior to the initiation of study treatment. If needed, the pregnancy testing at screening can be accepted for the entry value if the screening value was obtained within 72 hours of entry. All **participants** must begin treatment within 72 hours after **enrollment**.

6.2.3 Post-Entry Evaluations

On-Treatment Evaluations

Evaluations must occur after randomization. Study visits must be scheduled on the weeks indicated in section 6.1, within the visit windows.

The weeks 1 through 5 study visits must be scheduled per section 6.1, the SOE table \pm 3 days.

Please note influenza vaccination is prohibited \leq 7 days prior to all study visits. The study visit will need to be rescheduled if the influenza vaccine was given \leq 7 days prior to a study visit. All other vaccinations are prohibited throughout the duration of the study.

Post-Treatment Evaluations

There will be 7 additional weeks of follow-up after 5 weeks of study treatment. **Participants** will undergo evaluations as outlined at weeks 10 and 12 in section 6.1. The week 10 and 12 study visits must be scheduled per the SOE ± 7days. Week 12 is the final study visit.

NOTE: **Participants** who discontinue treatment prematurely are followed on study/off treatment until study completion, i.e., week 12.

Virologic Failure

For **participants** who have suspected virologic failure, based on an HIV-1 RNA level above the lower limit of quantification, the site should query the **participant** about intercurrent vaccination, acute illness, or identified periods of nonadherance. If one of these conditions is suspected to account for the increased HIV-1 RNA, then no further evaluation is necessary until the next study visit. If none of these factors are present, a confirmatory HIV-1 RNA should be done within 7 days of receipt of the results of the first test. If the repeat HIV-1 RNA is **below the assay limit of quantification**, then no further evaluation is necessary. See section 7.5 for management of confirmed virologic failure.

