9.0 STATISTICAL CONSIDERATIONS

9.1 General Design Issues

A5336 is a randomized (2:1), prospective, open-label, 2-arm pilot clinical trial designed to assess the safety and tolerability of ruxolitinib, and to evaluate whether 5 weeks of treatment with ruxolitinib decreases IL-6 levels in HIV-1 infected **participants** virally suppressed on ART. **Participants** will be randomized 2:1 to receive ruxolitinib or no study treatment. **Participants** receiving ruxolitinib will be followed on treatment for 5 weeks, then for an additional 7 weeks off treatment, resulting in a total 12 weeks of follow-up; **participants** receiving no study treatment will be followed on-study for 12 weeks. The total sample size will be 60 **participants**.

- 9.2 Objectives
 - 9.2.1 Primary Outcome Measures
 - 9.2.1.1 Safety

Occurrence of any one of the following safety milestones (from entry to week 5).

- For **participants** with entry CD4+ T cell count < 700 cells/mm³, confirmed CD4+ decline > 33% of baseline and to < 350 cells/mm³.
- For **participants** with entry CD4+ T cell count ≥ 700 cells/mm³, a confirmed CD4+ T cell decline > 50 % of baseline.
- Confirmed HIV-1 RNA level **above the lower limit of quantification** in the absence of an interruption in ART.
- New or recurrent CDC category C AIDS-indicator condition.
- HIV-1 associated infection including Varicella zoster.
- Lymphoproliferative malignancies.
- Discontinuation of ruxolitinib due to thrombocytopenia.
- Grade 4 or recurrence of Grade 3 anemia/neutropenia.
- Any Grade 4 or recurrence of Grade 3 toxicity related to study drug.
- New diagnosis of pneumonia, sepsis, or bacteremia.
- 9.2.1.2 Tolerability
 - Occurrence of premature discontinuation of study treatment.
- 9.2.1.3 IL-6

Participant-specific change in the level of plasma IL-6 (using geometric means of two ELISA measurements at pre-entry and entry, and weeks 4 and 5).

- 9.2.2 Secondary Objective Measures
 - 9.2.2.1 Proportion of **participants** who experienced any one of the primary safety milestones during total follow-up (from entry to week 12).
 - 9.2.2.2 Summary of safety laboratories at baseline and weeks 1, 2, 4, 5, 10, and 12.
 - 9.2.2.3 Change in the level of plasma IL-6 from baseline to weeks 4, 5, 10, and 12.
 - 9.2.2.4 Changes in soluble markers of immune activation and inflammation in the peripheral blood (sCD14, TNF- α , IL-1 α , IL-1 β , mCSF, and neopterin) from baseline to weeks 4, 5, and 12.

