- 9.2.2.5 Changes in cellular markers of immune activation and inflammation in the peripheral blood (HLA-DR, CD38, CD69 and CD14+/CD16+ monocyte levels) from baseline to weeks 5 and 12.
- 9.2.2.6 Changes in plasma HIV-1 RNA and CD4+ T cell counts from baseline to weeks 2, 5, and 12.
- 9.2.2.7 Changes in HIV-1 reservoir (HIV-1 RNA by SCA, cellular HIV-1 total RNA and DNA, 2-LTRs, integrated DNA) from baseline to weeks 5 and 12.

9.2.2.8 Level of HHV shedding (CMV, EBV, HHV 6, 7, 8) at pre-entry, entry, and weeks 1, 2, 4, 5, 10, and 12.

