9.5 Monitoring

Accrual and summary of all Grade ≥ 2 signs and symptoms, laboratory abnormalities and diagnoses, and all reported AEs will be reviewed by the team monthly. This summary will be pooled over the study arms. Baseline characteristics, early study treatment and study discontinuations, and virologic failures, pooled over study arms, will be reviewed regularly by the protocol team. In addition, data and specimen availability will be also regularly reviewed. The Statistical and Data Analysis Center (SDAC) will also prepare quarterly reports of all Grade ≥ 2 events, and all reported AEs by study arm, to be reviewed by the DAIDS clinical representative or designee.

An ACTG-appointed Study Monitoring Committee (SMC) will review accrual, toxicity summaries, off-treatment and off-study rates, and reasons broken down by study arms. An interim safety review by the SMC is planned at the earliest of 6 participants with 3 weeks of follow-up, 2 participants with Grade 3/4 toxicities, 3 participants discontinuing study treatment due to toxicities, or 3 months after the first participant enrolls. Subsequent SMC reviews are planned at approximately 6 month intervals, or in the event of 2 participants with Grade \geq 3 toxicities or 3 participants discontinuing study treatment due to toxicities in the interim.

In the event the SMC review is triggered due to toxicities (2 participants with Grade ≥ 3 toxicities or 3 participants discontinuing study treatment due to toxicities), accrual will be paused while the SMC review takes place. In addition, during the course of the study if any participant develops PML, or neurologic condition or dies of a drug-related adverse event, or if more than 2 participants, randomized to Arm A, experience confirmed virologic failure (see section 7.5 for definition) then dosing for all study participants will be stopped.

The team has requested the SMC consider the grade of the events, the time to resolution (if any), the temporal relationship to drug administration, and the site clinician's judgment of the relationship to treatment. The team would recommend particular review by the SMC if there were high occurrences of the safety events described in section 9.2.1.1.

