## 2.4 Outcome measures

### 2.4.1 Primary Outcome Measures

#### Safety

- 1) Proportion of participants on the *Ruxolitinib arm* who experience any of the following safety milestones while on-treatment:
  - o For participants with entry CD4+ T cell count  $< 700 \text{ cells/mm}^3$ , confirmed CD4+ decline  $> 33\%$  of baseline and to  $< 350 \text{ cells/mm}^3$ .
  - o For participants with entry CD4+ T cell count  $\geq 700 \text{ cells/mm}^3$ , a confirmed CD4+ T cell decline  $> 50\%$  of baseline.
  - o Confirmed HIV-1 RNA level above the lower limit of quantification in the absence of an interruption in ART.
  - o New or recurrent CDC category C AIDS-indicator condition.
  - o HIV-1 associated infection including Herpes zoster.
  - o Lymphoproliferative malignancies.
  - o Discontinuation of ruxolitinib due to thrombocytopenia.
  - o Grade 4 or recurrence of Grade 3 anemia/neutropenia.
  - o Any Grade 4 or recurrence of Grade 3 toxicity related to study drug.
  - o New diagnosis of pneumonia, sepsis, or bacteremia.
- 2) Proportion of participants who experience any of the following safety milestones on-study from entry through week 5 by study arm:
  - o For participants with entry CD4+ T cell count  $< 700 \text{ cells/mm}^3$ , confirmed CD4+ decline  $> 33\%$  of baseline and to  $< 350 \text{ cells/mm}^3$ .
  - o For participants with entry CD4+ T cell count  $\geq 700 \text{ cells/mm}^3$ , a confirmed CD4+ T cell decline  $> 50\%$  of baseline.
  - o Confirmed HIV-1 RNA level above the lower limit of quantification in the absence of an interruption in ART.
  - o New or recurrent CDC category C AIDS-indicator condition.
  - o HIV-1 associated infection including Herpes zoster.
  - o Lymphoproliferative malignancies.
  - o Occurrence of Grade 2 or higher thrombocytopenia.
  - o Grade 4 or recurrence of Grade 3 anemia/neutropenia.
  - o Any Grade 4 or recurrence of Grade 3 toxicity.
  - o New diagnosis of pneumonia, sepsis, or bacteremia.

- 3) Proportion of *each* of the following components that occurred on-study from entry to week 5 by study arm:
- o For participants with entry CD4+ T cell count  $< 700$  cells/mm^3, confirmed CD4+ decline  $> 33\%$  of baseline and to  $< 350$  cells/mm^3.
  - o For participants with entry CD4+ T cell count  $\geq 700$  cells/mm^3, a confirmed CD4+ T cell decline  $> 50\%$  of baseline.

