  - Confirmed HIV-1 RNA level above the lower limit of quantification in the absence of an interruption in ART.
  - New or recurrent CDC category C AIDS-indicator condition.
  - HIV-1 associated infection including Herpes zoster.
  - Lymphoproliferative malignancies.
  - Occurrence of Grade 2 or higher thrombocytopenia.
  - Grade 4 or recurrence of Grade 3 anemia/neutropenia.
  - Any Grade 4 or recurrence of Grade 3 toxicity.
  - New diagnosis of pneumonia, sepsis, or bacteremia.
- 4) Occurrence of protocol-defined reportable adverse events (all diagnoses, Grade 3 or higher sign/symptoms or laboratory values, any signs/symptoms or laboratory values that led to a change in treatment or met ICH, EAE, or SAE guidelines) at any post-entry time point.
- 5) Safety Laboratory values (estimated creatinine clearance, creatinine, AST (SGOT), ALT (SGPT), ANC, hemoglobin, platelet count) across all study weeks (at entry, week 1, and week 2, and arithmetic means at weeks 4 and 5, and at weeks 10 and 12).
- 6) Change in safety laboratory values (estimated creatinine clearance, creatinine, AST (SGOT), ALT (SGPT), ANC, hemoglobin, and platelet count) across all study weeks (at weeks 1 and 2, and arithmetic means at weeks 4 and 5 and at weeks 10 and 12).
- 7) Change in log10-transformed plasma IL-6 across all study weeks (geometric means of pre-entry and entry, and week 10 and 12).
- 8) Changes in soluble markers of immune activation and inflammation in the peripheral blood (sCD14, TNF- $\alpha$ , IL-1 $\alpha$ , IL-1 $\beta$ , IL-7, IL-10, IP-10, IL-18, mCSF, and neopterin) across study weeks from baseline (geometric mean of pre-entry and entry) to week 4/5 (geometric mean of week 4 and week 5) and week 12.

- 9) Changes in cellular markers of immune activation and inflammation in the peripheral blood (HLA-DR, CD25, CD38, CD69, CD127, Ki67, BCL2, a4b7, CX3CR1, PAR-1 measured on CD4 and CD8 cells; monocyte subsets (classical, inflammatory, and patrolling) defined by CD14 and CD16 expression; proportion of monocyte subsets (classical, inflammatory, and patrolling) expressing CCR2, CX3CR1, and CD163) from entry to weeks 5 and 12.
- 10) Level of plasma HIV-1 RNA at baseline and weeks 2, 5, and 12.
- 11) Change in CD4+ T cell counts from baseline (mean of pre-entry and entry) to weeks 2, 5, and 12.
- 12) Changes in HIV-1 reservoir (HIV-1 RNA by SCA, cellular HIV-1 total RNA and DNA) from entry to weeks 5 and 12.

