Confirmed virologic failure is defined as the occurrence of two sequential plasma HIV-1 RNA values above the lower limit of quantification in the absence of an interruption of ART; the confirmatory HIV-1 RNA should occur within 7 days of receipt of the results for the first test. In the event that a suspected virologic failure is not confirmed with a follow-up HIV-1 RNA test (i.e., there is no subsequent HIV-1 RNA available), this suspected virologic failure will be considered a *confirmed* virologic failure. Confirmed CD4 count decline is defined as two sequential CD4 counts meeting the respective criteria in the absence of an interruption in ART. Adverse events are classified as related (definitely, probably, possibly) or not related (probably not, not) by site investigators.

Biomarker data distributions will be assessed for normality, and any non-normal data will be log-transformed to the log-10 scale for analysis; it is anticipated that all soluble markers will be log-transformed. Descriptive summaries of continuous baseline characteristics will include frequency, frequency missing, mean, sd, median, IQR, 10th and 90th percentiles, and min/max; descriptive summaries of other continuous variables will use mean and sd, or median and IQR depending upon the corresponding analysis method. The frequency and percentage will be used for all categorical variables.

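### An open-label site may waive the 7-day repeat HIV-1 RNA until a visit that has none scheduled, so whether the same rise counts as confirmed virologic failure depends on site judgement

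*Protocol*

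**What the plan says.** **When a repeat is taken.** Under Protocol 6.2.3 (Virologic Failure), a value above the limit of quantification leads the site to ask about vaccination, acute illness and nonadherence. If none is present, "a confirmatory HIV-1 RNA should be done within 7 days of receipt of the results of the first test". If one is suspected as the cause, "then no further evaluation is necessary until the next study visit".

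**When visits and HIV-1 RNA are scheduled.** Post-entry visits fall at weeks 1, 2, 4, 5, 10 and 12 (Protocol 6.1; 9.2.2.2: "Summary of safety laboratories at baseline and weeks 1, 2, 4, 5, 10, and 12"). Post-entry HIV-1 RNA is scheduled at weeks 2, 5 and 12 (Protocol 6.1; 9.2.2.6: "Changes in plasma HIV-1 RNA and CD4+ T cell counts from baseline to weeks 2, 5, and 12"; SAP 2.4.2: "Level of plasma HIV-1 RNA at baseline and weeks 2, 5, and 12"). The schedule also has an HIV-1 RNA in a confirmation column tied to no week, and one at premature discontinuation.

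**What the endpoint is.** A primary safety milestone in SAP 2.4.1 is "Confirmed HIV-1 RNA level above the lower limit of quantification in the absence of an interruption in ART". Protocol 7.5 and SAP section 3 define confirmed failure as two sequential raised values without an ART interruption. SAP section 3 adds that "the confirmatory HIV-1 RNA should occur within 7 days of receipt of the results for the first test", and that a suspected failure with no later HIV-1 RNA is treated as confirmed.

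**Where it is used during the trial.** Protocol 7.5 attaches stopping of study drug in Arm A to confirmed failure. Protocol 9.5 stops dosing for all participants "if more than 2 participants, randomized to Arm A, experience confirmed virologic failure".

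**The concern.** The waiver is wider than the endpoint. The milestone recognises one exclusion, an interruption in ART. The waiver recognises three others, needs only suspicion, and is applied by a site that knows the arm. The visit it defers to has no scheduled HIV-1 RNA in the cases that matter for the primary window.

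Two participants with the same raised value can therefore be classified differently because one site drew a repeat and the other did not. That classification enters the primary safety composite in both arms and, through SAP section 3, removes participants with confirmed failure from the as-treated efficacy population. It also drives the in-trial actions in Protocol 7.5 and 9.5, where a counting rule applied at analysis comes too late.

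**Working it through.** **1. Follow a waived rise through the schedule (nominal weeks).**

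| Rise at | Next visit | HIV-1 RNA scheduled there? | Next scheduled HIV-1 RNA | Gap |
|---|---|---|---|---|
| Week 2 | Week 4 | No | Week 5 | 5 − 2 = 3 weeks |
| Week 5 | Week 10 | No | Week 12 | 12 − 5 = 7 weeks |
| Week 12 | None | – | None | – |

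The week 5 value falls at planned end of treatment. The week 12 value falls 7 weeks after it.

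**2. Classify each path under the stated definitions.**

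- Waived rise, next scheduled value suppressed: not two sequential raised values, so no event. A 7-day repeat might have confirmed it.
- Waived rise, next scheduled value raised: confirmed under Protocol 7.5, which sets no maximum interval. The SAP expects the repeat within 7 days and does not say whether a value 3 or 7 weeks later serves. A suppressed 7-day repeat could have separated two isolated rises.
- Waived rise, no later value: confirmed under SAP section 3.
- Week 5 rise confirmed at week 12: the SAP does not say whether this belongs to the entry-to-week-5 milestone.

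The first path loses events and the second and third can add them, so the net direction is open.

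**3. Reproduce the plan's safety power.** Inputs from Protocol 9.4.2: 40 vs 20, 27% vs 2%, one-sided Fisher, 5%. Power = Σₐ Σ_b Bin(a; 40, 0.27) · Bin(b; 20, 0.02) · 1{p(a,b) ≤ 0.05}, where p(a,b) = P(X ≥ a) and X is hypergeometric (60 participants, a+b events, 40 in Arm A). The result is 78.4%, against 80% stated, so the design figure is reproduced closely. With the SAP's mid-p test, which subtracts half of P(X = a), it is 88.9%.

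**4. What one participant can do.** With 0/20 in Arm B, the one-sided mid-p value is ½ · C(40,k)/C(60,k):

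- k = 6: ½ × 3,838,380 / 50,063,860 = 0.038
- k = 5: ½ × 658,008 / 5,461,512 = 0.060

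One event is 1/40 = 2.5 points in Arm A and 1/20 = 5 points in Arm B.

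**5. Ranges under assumptions.** The documents give no rate of low-level rises or of waivers, so these inputs are assumed.

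- Loss: if 10% to 50% of the 27% were virologic failure alone and 10% to 50% of those were missed, the observed Arm A rate is 27% × (1 − 0.1 × 0.1) = 26.7% down to 27% × (1 − 0.5 × 0.5) = 20.3%. Mid-p power falls from 88.9% to between 88.4% and 68.6%.
- Gain: if 2, 5 or 10 points of unconfirmed rises were added to both arms, mid-p power is 83.3%, 76.5% or 68.2%.
- Protocol 9.5 rule, P(at least 3 of 40), at assumed true failure rates of 5%, 10% and 15%: 0.323, 0.777 and 0.951 with none missed; 0.078, 0.323 and 0.586 with half missed.

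**The case against.** A reader might infer that virologic failures are under-counted overall. The documents do not support that. The SAP counts a rise with no later value as confirmed, and a later raised scheduled value can be the second of two. Protocol 6.2.3 already treats a rise with a suppressed repeat as needing nothing further. The loss is confined to rises that a 7-day repeat would have confirmed but that had resolved by the later draw.

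A reader might also infer that events are lost preferentially in Arm A, since infection is a named ruxolitinib risk and acute illness is a ground for waiver. This is possible but not shown. The waiver covers both arms, and pneumonia, sepsis, bacteremia and HIV-associated infections including zoster are themselves milestones, so those participants still count in the composite. Only milder illness could produce the effect, and no figure in the documents bears on it.

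Other points stand in part:

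- SAP 4.2.2 tabulates HIV-1 RNA above or below the limit by week and arm, and requires a narrative for anyone with a raised value on study. Waived rises stay visible, but the milestone is not reclassified.
- The vaccination ground should seldom apply. Non-influenza vaccines are prohibited on study, and visits are rescheduled after a recent influenza vaccine.
- The waiver could be read as resuming evaluation at the next visit through the unscheduled confirmation column. The text does not say so, and sites may read it either way.
- The comparison of 6/40 with 5/40 is a chosen edge case. It shows fragility near the threshold, as it would for any component, and not likely impact.

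**Conclusion.** The point holds as a conflict between the waiver, the visit schedule, the endpoint definition and the SAP. Followed as written, Protocol 6.2.3 makes a primary safety milestone depend on unblinded site judgement and leaves 3 or 7 weeks to the next scheduled HIV-1 RNA. This assumes nominal visit weeks and no unscheduled or discontinuation draw in between.

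The effect on the composite may be small, and its direction and size cannot be set from the documents; the ranges above rest on assumed rates. The in-trial consequence is firmer. After a waived week 2 rise, the next scheduled value coincides with planned end of treatment, so confirmation under Protocol 7.5 can come with no planned treatment time left. Confirmation for the Protocol 9.5 rule is delayed in the same way, and the SAP's rule for rises without a later value cannot repair either. The issue should be settled, but it does not invalidate the safety comparison.

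**What to change.** - Reconcile Protocol 6.1, 6.2.3, 7.5 and 9.5 with SAP section 3 on when a raised value is retested and what counts as confirmation.
- For endpoint ascertainment, collect the confirmatory HIV-1 RNA on the same basis in both arms, using the confirmation column already in the schedule. Record suspected illness, vaccination or nonadherence as explanatory data, and apply the ART-interruption exclusion in the analysis.
- State in the SAP how a later scheduled value is treated after a rise without a 7-day repeat, and whether a week 5 rise confirmed at week 12 belongs to the entry-to-week-5 milestone. The same dating rule should cover an on-time repeat, which after a week 5 rise can also fall past the week 5 visit.
- What follows for stopping of treatment under Protocol 7.5 and 9.5 is for the sponsor to reconcile; no clinical rule is proposed here.

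The cost is protocol and SAP wording, plus a few extra blood draws among participants with a raised value.

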6.2.4 Discontinuation Evaluations

Evaluations for Randomized or Registered **Participants** Who Do Not Start Study Treatment

All CRFs must be completed and keyed for the period up to and including entry. No further follow up is required for **participants** randomized to Arm A who do not start study treatment.

Premature Treatment Discontinuation Evaluations

Participants who prematurely discontinue the study treatment prior to week 5 should complete the premature treatment discontinuation evaluations within 14 days after discontinuing treatment. **Participants** will then be followed on study/off study treatment.

Site personnel should notify the protocol core team ([contact]) within 48 hours of any **participant** who prematurely discontinues the study treatment.

Premature Study Discontinuation Evaluations

Participants who prematurely discontinue the study will have the premature treatment/study discontinuation evaluations performed prior to being taken off the study.

Site personnel should notify the protocol core team ([contact]) within 48 hours of any **participant** who prematurely discontinues the study.

Pregnancy

Pregnancy will result in immediate and permanent discontinuation of the study treatment. Please see section 7.4 for detailed information regarding **participant** management.

